Cover Page

Double sequence external defibrillation:
A randomized controlled trial in
patients with atrial fibrillation
refractory to DC cardioversion

Date: 31/1/2019

NCT ID not yet assigned

Background information and Significance

Atrial fibrillation (AF) is the most common sustained cardiac arrhythmia in clinical practice. Patients are at increased risk for death, heart failure, hospitalization, and thromboembolic events [1-3]. In one study by Go et al., it was shown that the overall prevalence of AF was 1%; ranging from 0.1% among adults less than 55 years of age to 9% in those ≥ 80 years of age [4]. The restoration (cardioversion) of sinus rhythm is performed in many patients with AF to improve symptoms. Therefore, some physicians attempt to restore sinus rhythm ('rhythm control' strategy) in patients with AF, either using drugs ('pharmacological cardioversion') or by direct current (DC) shocks ('electrical cardioversion'). Electrical cardioversion requires admission to the hospital, a short-acting anesthetic and a direct current shock. Sometimes repeated cardioversions are required if a patient spontaneously reverts to AF. There are two important reasons why cardioversion might be useful. Firstly, successful restoration of sinus rhythm may reduce the risk of embolic complications, thereby obviating the need for long term anticoagulation, with its attendant risks [5]. Secondly, observational studies have shown that after successful restoration of sinus rhythm, left ventricular function improves [6], atrial and ventricular function normalizes [7], and that after restoration of atrial contractility, left ventricular ejection fraction and maximal exercise capacity both improve [8]. Electrical cardioversion (ECV) is the standard treatment for acute AF, but identification of patients with increased risk of ECV failure or early AF recurrence is of importance for rational clinical decision-making. A study by Jaakkola et al. showed that the risk of unsuccessful outcome of Electrical Cardioversion (ECV) can be predicted using 5 simple clinical variables: age, whether or not it is the first AF, cardiac failure, vascular disease and whether or not there's a short interval from the previous AF episode [9]. In obese patients for instance, high impedance can also decrease the effective energy delivered to the atria in large-bodied patients [10]. AF has been treated with DC shocks delivered trans-thoracically, but in 5-30% of patients, the procedures fail to restore sinus rhythm (SR) [11]. Higher energy external DC cardioversion (DCC) has long been used for ventricular arrhythmias [12, 13]. There have been some studies that have reported on the delivery synchronized higher energy external DCC as an alternative approach for cardioversion in patients with AF refractory to conversion with standard external cardioversion energies [14, 15].

A study by Saliba et al. in 1999 showed that external higher energy cardioversion is effective in restoring sinus rhythm in patients with AF refractory to standard energy DC cardioversion

and that this method is safe and does not result in clinical evidence of myocardial impairment [15].

Despite the benefit shown, this study was conducted 19 years ago and the practice was not implemented as a standard of care. The investigators would therefore like to revisit the evidence behind the effectiveness of double sequential defibrillation. The investigators hope to prove the benefit behind this intervention and ultimately disseminate the findings through international conferences.

The investigators hypothesize that applying high energy shock waves to the chest through double sequential external defibrillation (DSED) may overcome the inadequate penetration of electrical shock to the atrium and restore SR more effectively than DC cardioversion, after two attempts of DC cardioversion.

Specific aims

Objectives

The objective of this study is to assess the effectiveness of double sequence defibrillation in reverting patients with AF refractory to two trials of direct current cardioversion.

Hypothesis

In patients with AF refractory to 2 or more trials of DC cardioversion, the use of double sequential defibrillation has a higher success rate in terms of reverting patients to sinus rhythm as compared to an additional trial of DC cardioversion.

Research design and methods

a) Study design and setting

This study is a Phase III, randomized controlled, superiority trial, with two parallel groups, conducted in one academic medical center. The study will be conducted in a 376-bed, tertiary care academic hospital (American University of Beirut Medical Center) for a period of 5 years. It will take place in a 22-bed Coronary Care Unit (CCU), which is run as a closed unit by onsite coverage 24-hr/7 days, under the care of 16 cardiologists.

b) Inclusion/exclusion

Mainly, all AF patients admitted to the CCU for DC cardioversion, and refractory to at least two trials of DC cardioversion will be eligible for this study. Excluded from this study will be patients with AF not requiring DC cardioversion, or those with AF who reverted after a maximum of two trials of DC cardioversion.

c) Sampling

Patients presenting to the CCU with persistent AF for direct current (DC) cardioversion, who meet the inclusion criteria and fail to revert to normal sinus rhythm after two DC cardioversion attempts will be invited for enrollment in the study. No sampling will be carried out for the sake of this study.

d) Intervention

Patients meeting the eligibility criteria will receive double sequential defibrillation (DSED) or a third DC cardioversion (standard of care).

DSD is the process of using two defibrillators near simultaneously at their highest allowed energy setting and aims to treat refractory AF. The first set of pads is placed in the traditional anterolateral position and the second set can be either placed adjacent to the first set (anterolateral) or in the antero-posterior position. Shocks are then delivered simultaneously or near simultaneously [16].

e) Randomization:

Randomization will be performed as permuted block randomization. Blocks of different sizes will be used as the randomization unit for the purpose of randomization. More specifically, block sizes of 4, 6 and 8 will be used. Computer generated randomization list will be provided by the statistician.

f) Allocation concealment:

To minimize selection bias in the study due to the allocation knowledge of the recruiting personnel, allocation concealment will be adopted in this study. Accordingly, the RAs who are responsible for recruiting patients into the study will use sealed opaque envelopes where the allocation would be specified within. When a patient meets the inclusion criteria, and consents to the study, the next envelope in place will be opened to identify the allocation of this patient into the intervention or control group.

g) Outcome

The investigators' outcome measure will be the number of participants with atrial fibrillation who revert to normal sinus rhythm using DSED after two failed attempts of DC cardioversion. This will be determined by conducting an Electrocardiogram (EKG) immediately after DSED. The EKG will be read by a trained physician to determine if the patient has successfully reverted to sinus rhythm.

h) Other factors and data collection

A data collection form (Appendix 1) will be used to collect information about the subject. This information will be obtained by the research fellow during his private interview with the patient after consent is taken. Some data will also be obtained from the electronic health records by the same CITI certified research fellow. Data will be related to AF and to the risk stratification tool (AFCVS score). Variables include demographics (age, gender), metrics (BMI, waist-hip ratio), past medical history (hypertension, diabetes mellitus, etc.), past surgical history (CABG, PCI, etc.), medications, social history, vital signs, physical exam, echocardiography results, NYHA score.

i) Sample size

There are no similar studies published in the literature assessing the efficacy of DSED on refractory AF. Accordingly, for the purpose of sample size calculation, the investigators considered a conservative approach in the calculation. More specifically, the investigators considered that 50% of patients with refractory AF will revert to sinus rhythm after 3 trials of DC cardioversion. Based on clinical experience, the investigators expect 78% to achieve

positive outcome after 2 trials of DC cardioversion followed by a third trial of DSED. This will yield an expected difference of 28% in DSED between the intervention and control groups. Considering a power of 80% and an alpha of 0.05, the investigators will require 50 patients in each arm, a total of 100 patients.

j) Statistical analysis

In the univariate analysis, the distribution will be presented as means \pm standard deviations and frequencies (percentage) for the continuous and categorical variables, respectively. In the bivariate analysis, student's t-test and Pearson's chi-square test will be used to assess the significance of the statistical association between the independent variables (continuous and categorical) and the two groups (Intervention and control) of the outcome. Furthermore, results will be presented as odds ratios (OR) and their corresponding 95% confidence intervals (CI).

A multivariate analysis will be carried out for the association between the intervention and outcome, while controlling for potentially confounding variables. More specifically, multivariate logistic regression analyses will be carried out. A stepwise selection procedure will be used including all risk factors found to be statistically significant at the bivariate level in addition to those considered as being clinically meaningful. Similarly, results will be presented as OR and their corresponding 95% CI.

The primary analysis is an intention-to-treat analysis (ITT) of unadjusted results. ITT being defined as analysis of all participants as randomized, regardless of whether the participants respected the study protocol or not (effectiveness). Sensitivity analysis will be carried out as per-protocol analysis consisting of analyzing individuals according to the treatment that the participants took, independently of their randomization.

P-values will be considered statistically significant if ≤ 0.05 . SPSS version 25.0 will be used to carry out the data cleaning, management and analyses.

Ethical considerations

The RA will consent patients, right after the cardiologist consents for the standard DC cardioversion procedure, using lay language prior to cardioversion. The risks and benefits of DC cardioversion and double sequential external defibrillation, as well as alternatives to their use will be thoroughly described. A copy of the informed consent will be given to each participant.

Data collection will be carried out by CITI certified research assistants. Only the information in patient charts and records will be observed and recorded. This study will not in any way influence the decision-making process or actions of AUBMC staff treating the patient.

All data collected will be stored in a manner that restricts identifiers to the PI and on a need to know basis for other researchers, and in keeping with the ten-year safe and secure storage regulations. All data will be entered in an excel sheet located on a password-protected computer of the primary investigator. After completion of the analysis, all patient identifiers located on the excel document will be removed.

Time frame

The study is expected to start in winter 2018 and will extend over 7 years: one year for study implementation, 5 years for patient recruitment and one year for data analysis and manuscript write up. It is projected to end in winter 2025.

References

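### Does taking consent before cardioversion but inviting patients only after two failed shocks leave the point of randomisation open?

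*Combined protocol and SAP*

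**What the plan says.** Five places in the combined protocol and SAP bear on the order of events.

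- **c) Sampling:** patients with persistent AF "who meet the inclusion criteria and fail to revert to normal sinus rhythm after two DC cardioversion attempts will be invited for enrollment".
- **Ethical considerations:** "The RA will consent patients, right after the cardiologist consents for the standard DC cardioversion procedure, using lay language prior to cardioversion".
- **b) Inclusion/exclusion:** AF patients "refractory to at least two trials of DC cardioversion will be eligible for this study"; excluded are "those with AF who reverted after a maximum of two trials of DC cardioversion".
- **f) Allocation concealment:** "When a patient meets the inclusion criteria, and consents to the study, the next envelope in place will be opened".
- **h) Other factors and data collection**, on the data form: "This information will be obtained by the research fellow during his private interview with the patient after consent is taken".

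The background section adds that "Electrical cardioversion requires admission to the hospital, a short-acting anesthetic and a direct current shock". Section j) Statistical analysis defines the primary analysis as intention-to-treat on all randomised participants.

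**The concern.** Read alone, section c) has staff first approach a patient after the second failed shock. Ethical considerations has them do so before the first. If c) were followed literally and all shocks fell in one session, consent would be sought from someone who has just had an anesthetic, or the next shock would wait for recovery. The first raises doubt about the consent; the second could select who enters.

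The envelope is the weightier matter. Section f) names no shock number, and c) lists meeting the inclusion criteria and failing two shocks as if they were separate conditions. A reader could then wonder whether a patient who consents beforehand might be randomised beforehand too. With an intention-to-treat analysis, that would bring in patients who convert on the first or second shock and never receive the randomised treatment, and the treatment difference would be diluted.

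**Working it through.** **1. The plan's own sample size.** Inputs from section i): 50% control, 78% DSED, alpha 0.05, power 80%, 50 per arm. Sidedness is not stated; two-sided is assumed here. With the pooled-variance formula, mean proportion 0.64 and difference 0.28:

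n = [1.960 × √(2 × 0.64 × 0.36) + 0.842 × √(0.50 × 0.50 + 0.78 × 0.22)]² / 0.28² = 45 per arm after rounding up.

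With a continuity correction this becomes 52. The stated 50 lies between the two, and 50 per arm without correction gives 84.1% power. These rates describe patients already refractory to two shocks, so the calculation presupposes randomisation after the second failure.

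**2. What early opening would cost.** Suppose, contrary to the natural reading, that envelopes were opened before the first shock. Let f be the share of consented patients who fail two shocks, and count the rest as converted in both arms. Then:

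- control rate = (1 − f) + 0.50f
- DSED rate = (1 − f) + 0.78f
- difference = 0.28f

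The documents do not give f. The background section's 5-30% failure range is used as a stand-in.

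| f | Control | DSED | Difference | Power at 50 per arm |
|---|---|---|---|---|
| 5% | 97.5% | 98.9% | 1.4 points | 7.6% |
| 10% | 95.0% | 97.8% | 2.8 points | 11.3% |
| 20% | 90.0% | 95.6% | 5.6 points | 18.9% |
| 30% | 85.0% | 93.4% | 8.4 points | 27.0% |
| 100% (opened after second failure) | 50.0% | 78.0% | 28.0 points | 84.1% |

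So the moment of opening matters a great deal. The question is whether the plan leaves it open.

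**3. Whether it does.** Section f) requires two things before an envelope is opened: the inclusion criteria are met, and consent has been given. Under section b), a patient is not eligible until at least two shocks have failed, and anyone who converted within two is excluded. The first requirement therefore cannot be satisfied before the second failure, whenever consent was taken. Only the last row of the table is compatible with b) and f).

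**4. When consent is taken.** Ethical considerations is the only text that gives consent a time. Section c) describes who enters the trial. Taking consent beforehand and enrolling once two shocks have failed satisfies b), f) and Ethical considerations. It strains only the choice of verb in c).

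**5. Consent workload.** Consents needed for 100 randomised patients = 100/f, ignoring refusals and withdrawals: 100/0.30 = 334 (rounded up) to 100/0.05 = 2,000. Over five recruitment years that is 67 to 400 a year, with 70% to 95% of those consented never randomised. This is the cost of consenting before the procedure, which the plan already specifies. It does not measure harm from the wording of c).

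**The case for a change.** The strongest case for a change is that consent and randomisation are where a protocol should not make staff infer the order of events. To be invited ordinarily means to be asked, and someone who has already consented needs no invitation. A research assistant working from c) alone could make the first approach in the middle of the procedure. The remedy would be cheap: a sentence in c) and f), and perhaps a log of patients who consented but were not randomised.

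The textual point stands: c) and Ethical considerations are not expressly reconciled. The consequences drawn from it are weaker.

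- **Anesthetic.** This problem needs c) to override the only section that times consent. It also needs all the shocks to fall in one session. Section c) can be read that way, but no section says so outright.
- **Interview.** It might seem to have no slot before the third shock, but section h) places it only after consent and sets no such deadline. Some data also come from the electronic record.
- **Selection.** If recovery or willingness after two shocks filtered who entered, that would happen before a sealed, opaque envelope was opened. It could narrow the population represented. It would not make the arms differ systematically, and its size cannot be computed from the documents.
- **Log.** This would be useful for reporting, but it is not needed to reconcile the sections and alters no analysis.

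**Conclusion.** No change to the plan follows. The mismatch between c) and Ethical considerations is real but is one of wording. Sections b) and f) already place the opening of the envelope after the second failed shock, and Ethical considerations already places consent before the procedure. Writing that sequence out in one sentence would leave the randomised set, the primary analysis, the sample size and the conclusion as they are. The authors may tidy the verb in c) at a convenient revision, but nothing depends on it.

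No loss of power is shown: about 84% at 50 per arm under the operative reading. The low-power rows in the table belong to a sequence that b) and f) exclude.

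This rests on three assumptions: staff apply b) as written when they judge eligibility under f); concealment by sealed envelopes holds; and the 5-30% background range, used only for illustration, is a fair stand-in for the share failing two shocks. The conclusion does not depend on the third.

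### The plan gives 50 patients a highest-energy double shock over 5 years and describes no collection of harms, no review of harm counts by arm and no trigger to pause randomisation

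*Combined protocol and SAP*

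**What the plan says.** Section d) Intervention describes the experimental arm: "DSD is the process of using two defibrillators near simultaneously at their highest allowed energy setting and aims to treat refractory AF". Section i) Sample size sets the exposure: "the investigators will require 50 patients in each arm, a total of 100 patients". The Time frame section gives the order of work: "one year for study implementation, 5 years for patient recruitment and one year for data analysis and manuscript write up".

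Section g) Outcome names one outcome, sinus rhythm on an EKG taken immediately after the shock. Section h) lists demographics, body measurements, history, medications, examination, echocardiography and NYHA score, and names no post-shock event. Section j) describes an unadjusted intention-to-treat analysis, a per-protocol sensitivity analysis and regression models, with no interim look. Ethical considerations covers consent (including a description of risks), data access and storage.

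On prior safety, the background says of a 1999 study of higher-energy cardioversion that "this method is safe and does not result in clinical evidence of myocardial impairment". It also cites reference 14, whose title calls dual 360-J shocks in refractory AF safe and effective. Reference 11 is, by its title, another double-shock study in refractory AF.

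**The concern.** The plan describes three things that a monitoring arrangement needs in none of its sections: harm data, someone who counts them by arm while patients are being randomised, and a condition that prompts a pause. The first scheduled work on the data comes after recruitment has ended.

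At even recruitment, 50 DSED patients over 5 years is 50/5 = 10 a year. Events that arrive slowly are hard to recognise as an excess unless someone adds them up and sets them against the control arm. If serious events were more frequent under DSED, the investigators and the ethics board would have no tabulated evidence to act on. Monitoring that was never set up cannot be supplied after the last patient has been treated.

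**Working it through.** **1. The exposure figure.** Section i) assumes 50% v 78% conversion, and says: "Considering a power of 80% and an alpha of 0.05". Two-sided testing is assumed, as sidedness is not stated. With mean proportion 0.64 and difference 0.28:

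n = [1.960·√(2·0.64·0.36) + 0.842·√(0.50·0.50 + 0.78·0.22)]² / 0.28² = (1.330 + 0.546)² / 0.0784 ≈ 44.9, so 45 per arm.

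The continuity correction, n/4·[1 + √(1 + 4/(0.28n))]², gives 52. At 50 per arm, power is 84.1% by the uncorrected chi-square test and 78.9% by Fisher's exact test. The planned 50 lies between the two calculations and is taken as the DSED exposure.

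**2. Expected events without a review.** The documents give no harm rate, so p is assumed. Expected events are 50p; the chance of at least one is 1 − (1 − p)^50.

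| Assumed rate | Expected events in 50 | P(at least one) |
|---|---|---|
| 2% | 1 | 64% |
| 5% | 2.5 | 92% |
| 10% | 5 | 99.5% |
| 20% | 10 | >99.9% |

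At 10%, the chance of at least one event in the first 10 DSED patients is 1 − 0.9^10 = 65%, so a signal could appear early.

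**3. What a harm-only rule could do (illustration).** Looks come after 10, 20, 30 and 40 DSED patients. For a reference rate p0 and prior Beta(p0, 1 − p0), the posterior after k events in n patients is Beta(p0 + k, 1 − p0 + n − k). The rule pauses at the smallest k for which the posterior probability that the rate exceeds p0 is above 0.95. For p0 = 2% and n = 10, that probability is 0.825 at k = 1 and 0.985 at k = 2, so the first boundary is 2.

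- 2% reference: boundaries 2/3/3/3.
- 5% reference: boundaries 3/4/5/5.

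Pause probabilities come from exact binomial recursion over the looks. For the 2% reference at a true rate of 10%, the first look gives 1 − 0.9^10 − 10·0.1·0.9^9 = 0.264. The four looks give 0.2639 + 0.1267 + 0.2216 + 0.1732 = 0.785. Mean DSED exposure is 10·0.2639 + 20·0.1267 + 30·0.2216 + 40·0.1732 + 50·0.2146 = 29.5 patients.

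| True rate | P(pause), 2% reference | Mean exposed | P(pause), 5% reference | Mean exposed |
|---|---|---|---|---|
| 1% | 1.1% | 49.7 | 0.02% | 50.0 |
| 2% | 5% | 48.8 | 0.2% | 49.9 |
| 5% | 34% | 42.4 | 6% | 48.8 |
| 10% | 79% | 29.5 | 39% | 41.7 |
| 20% | 99% | 16.0 | 93% | 23.6 |

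Mean exposure assumes that recruitment ends at the pause. Expected events up to that point are mean exposure × rate. At 20% they fall from 10 to 16.0 × 0.20 = 3.2 (2% reference) or 23.6 × 0.20 = 4.7 (5% reference). At 10% they fall from 5 to 2.9 or 4.2.

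**4. Effect on the efficacy test.** Looks that count harms only, withhold conversion rates and can only pause enrolment give no chance to claim efficacy early. They spend no alpha, and 50 per arm need not change.

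**The case against.** A reader might infer that a harmful arm is certain to run to full size. The documents do not support that: the plan is silent on stopping and does not tell anyone to continue. Treatment takes place in one closed unit with round-the-clock onsite cover and no blinding is described, so staff could see a serious event around the shock and know the arm. An ad hoc stop is possible. What stands is that bedside cover looks after each patient and does not compare arms, and that the plan provides no counts for such a decision.

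A reader might also infer that DSED is untested or hazardous, especially from section i): "There are no similar studies published in the literature assessing the efficacy of DSED on refractory AF". That sentence concerns efficacy, and it sits uneasily with references 11 and 14, whose titles describe double shocks in refractory AF. One study is called safe in the text and another in its title. This lowers the expectation of harm; it does not replace counting.

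A third objection is that a trigger helps only when harm is common. This is partly right. The 5% reference rule pauses with probability 0.02% at a true rate of 1%, 0.2% at 2% and 1.0% at 3%, and misses a true rate of 10% in 61% of trials. The reference rate decides how useful the rule is, so its behaviour at low rates has to be shown.

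Also, both arms have already had failed shocks, so background events could trip a boundary set on the DSED count alone; the control count must be seen beside it. Finally, Appendix 1 is not in the supplied text and might list complications. A list would supply part of the data, but not a review schedule or a trigger.

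**Conclusion.** The concern holds as a gap in monitoring, and the plan should be changed. The supplied text has no harm collection, no review of counts by arm and no pause trigger for 50 patients treated over 5 years. It does not follow that DSED is harmful or that nobody would stop the trial.

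The size depends on assumed rates. At a true serious-event rate of 10%, an illustrative rule would cut mean DSED exposure from 50 to 29.5 patients (2% reference) or 41.7 (5% reference). At 1% to 2% it would change almost nothing. These figures assume independent events at a constant rate, looks at exactly 10, 20, 30 and 40 DSED patients, and complete event recording.

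**What to change.** Add to the data form a short pre-listed set of serious procedure-related events, recorded in both arms from the chart by the existing research staff. This comes first, because without it there is nothing to count.

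Add a monitoring paragraph to the design section. After every 10 DSED patients (about yearly at even recruitment), the existing statistician gives the principal investigator and the ethics board cumulative event counts for both arms, with conversion rates withheld. Randomisation pauses for their review if the DSED count reaches a boundary fixed before the first patient. Failure to convert and AF recurrence are not counted as events.

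The investigators choose the event list and the reference rate. The statistician derives the boundary and prints its operating characteristics, including at low true rates. The boundaries above are illustrations, not recommended values. A reviewer independent of the investigators would strengthen the arrangement but is not essential to it.

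Cost: one added form field, one protocol paragraph and about four tabulations, with no extra patients. In the illustrations the chance of an unneeded pause is about 5-6% when the true rate equals the reference rate. The principal investigator would also see harm counts by arm, in a trial that describes no blinding.

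### Section g) does not require the physician who reads the only outcome EKG to be masked to arm or independent of the operator

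*Combined protocol and SAP*

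**What the plan says.** All references are to the lettered parts of Research design and methods in the combined protocol and SAP, unless stated otherwise.

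- **Outcome, g).** One outcome is defined: "outcome measure will be the number of participants with atrial fibrillation who revert to normal sinus rhythm using DSED". It is established by "conducting an Electrocardiogram (EKG) immediately after DSED", and "The EKG will be read by a trained physician to determine if the patient has successfully reverted to sinus rhythm". The reader's relation to the treating team, a second reader, adjudication and a minimum duration of sinus rhythm are not mentioned. The EKG is timed for DSED only.
- **Intervention, d).** Patients "will receive double sequential defibrillation (DSED) or a third DC cardioversion (standard of care"). DSED is described as "using two defibrillators near simultaneously at their highest allowed energy setting", with two sets of pads.
- **Allocation concealment, f).** After eligibility and consent, "the next envelope in place will be opened to identify the allocation of this patient into the intervention or control group". The stated purpose is to limit selection bias.
- **Statistical analysis, j).** The primary analysis is the unadjusted intention-to-treat comparison, with significance at p ≤ 0.05. An adjusted model and a per-protocol analysis are also planned.

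The documents nowhere mention blinding or masking of patients, operators, EKG readers or the analyst.

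**The concern.** Anyone at the bedside will know which procedure was given. The EKG follows at once, so the convenient reader is someone who was there. As g) is worded, that could be the operator. The envelopes do their work up to the moment they are opened and do not protect what happens afterwards.

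If a reader who knows the arm resolves doubtful tracings in favour of DSED, the only efficacy estimate is biased and the false-positive rate rises. The adjusted and per-protocol analyses would not show this, because they use the same readings. The background section says that "The investigators hope to prove the benefit behind this intervention". That is an ordinary expectation and no evidence about the reader, but masking exists to guard against such expectations.

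**Working it through.** **Inputs from the plan.** Section i) assumes for control that "50% of patients with refractory AF will revert to sinus rhythm after 3 trials of DC cardioversion". It expects 78% with DSED and sets power 80%, alpha 0.05 and 50 per arm. Section j) names Pearson's chi-square test. A two-sided test is assumed, since sidedness is not stated.

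**Reproducing the plan's sample size.** With d = 0.28 and mean rate 0.64:

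n = [1.96·√(2·0.64·0.36) + 0.8416·√(0.50·0.50 + 0.78·0.22)]² / 0.28² = (1.3305 + 0.5465)² / 0.0784 ≈ 44.9, so 45 per arm.

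With continuity correction the figure is 52. The stated 50 is within two patients of that. At 50 per arm the exact power of the uncorrected Pearson test is 84.3%. Nothing below depends on disputing the sample size.

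**Effect of arm-dependent misreading when there is no true difference.** Let both true rates be 50%, and let f be the assumed share misread. The observed rates become:

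- DSED failures read as sinus rhythm: 0.5 + 0.5f
- Control conversions read as AF (second scenario only): 0.5(1 − f)

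The rejection rate is the sum, over all pairs (a, b) of observed control and DSED successes, of Bin(a; 50, control rate) × Bin(b; 50, DSED rate) wherever

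|a − b|/50 ÷ √(2·p̄(1 − p̄)/50) ≥ 1.96, with p̄ = (a + b)/100.

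| Share f (assumed) | DSED arm only: observed rates (DSED v control) | Two-sided rejection | Favouring DSED | Both arms: observed rates (DSED v control) | Two-sided rejection | Favouring DSED |
|---|---|---|---|---|---|---|
| 0 | 50% v 50% | 5.7% | 2.8% | 50% v 50% | 5.7% | 2.8% |
| 2% | 51% v 50% | 5.8% | 3.6% | 51% v 49% | 6.2% | 4.4% |
| 5% | 52.5% v 50% | 6.5% | 4.9% | 52.5% v 47.5% | 8.8% | 8.0% |
| 10% | 55% v 50% | 8.8% | 8.0% | 55% v 45% | 18.5% | 18.3% |

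The baseline for comparison is 5.7%, not the nominal 5%, because the uncorrected Pearson test is slightly liberal at this size. With 25 expected failures in the DSED arm, f = 2%, 5% and 10% mean on average 0.5, 1.25 and 2.5 misread tracings there. At f = 10% the spurious difference is 5 points (DSED arm only) or 10 points (both arms), against the planned 28.

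**How many readings matter.**

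- Planned result, 39/50 v 25/50: z = 0.28/√(0.64·0.36·0.04) = 2.92, p = 0.0035.
- Five DSED readings changed to failure, 34/50 v 25/50: z = 0.18/√(0.59·0.41·0.04) = 1.83, p = 0.067.
- From a tie of 25/50 in each arm, significance first appears at 35/50: z = 0.20/√(0.60·0.40·0.04) = 2.04, p = 0.041. That takes ten false readings among 25 DSED failures, or 40%.

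**The case against.** Four points can be made on the other side.

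1. **The documents are silent.** A reader might infer that the trial is unblinded and the EKG reader unmasked. The text does not say so; it names a trained physician and stops. What it supports is that masking and independence of the reader are not required and that the arms are distinguishable at the bedside. This limits the claim but leaves the gap, since a safeguard that is not written down cannot be relied on.
2. **The reading is fairly objective.** AF against sinus rhythm on a recorded tracing leaves less room than a symptom score, and the documents do not describe these tracings as hard to read. This stands, and it is why the small shares in the table deserve most weight. Against it, g) sets no duration of sinus rhythm, which leaves some room for judgement.
3. **The threshold argument is easily overdone.** Against 25/50 in control, 34/50 is not significant and 35/50 is, so a reader might infer that one tracing decides the trial. That is true of any fixed threshold and only when the result happens to lie there. The planned result needs five changed readings, and an exact tie needs ten.
4. **The two-arm scenario is the harsher one.** It requires genuine control conversions to be called AF as often as DSED failures are called sinus rhythm. Over-calling DSED success alone is simpler and gives much smaller inflation. Both are shown for that reason.

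**Conclusion.** The gap is real and its likely effect is modest. Section g) permits arm-dependent reading of the only outcome, and nothing else in the plan could detect it. On assumed misreading shares of 2% to 10%, two-sided rejection under no true difference moves from 5.7% to between 5.8% and 8.8% if only DSED failures are misread, or to between 6.2% and 18.5% if control conversions are misread as well. Rejections in favour of DSED rise from 2.8% to 4.9% or 8.0% at a 5% share.

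These figures rest on true rates of 50% in both arms, 50 patients per arm, the uncorrected Pearson test and shares that come from no source in the documents. They do not show that bias will occur or that it would decide the result. This is a cheap improvement to the plan, not a defect that invalidates it.

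**What to change.** Amend g) to state that:

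- the post-shock EKG is recorded at the same point after the randomized shock in both arms, since the text now times it for DSED only;
- each tracing is coded and stripped of allocation and operator notes;
- the trained physician already named in g) reads it for the primary outcome, was not present at the procedure and does not know the arm;
- the primary analysis uses this masked reading, and the bedside reading serves care only.

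Absence from the procedure matters, because someone who was there may recognise the case even from a coded tracing. Section a) gives the unit 16 cardiologists, so this should be a matter of assigning an existing role, not adding a reader.

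The cost is a few sentences, the coding of about 100 tracings and a research reading that comes later than the bedside one; reading in batches is acceptable. No procedure is added, and the sample size and planned power (84.3% by the exact Pearson calculation) are unchanged. One limit remains: masked reading cannot correct a biased bedside choice of which tracing to keep, which is why the common recording point belongs in the same amendment.
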